POC Point-of-Care Veritor COVID-19 Test

PREDICT Pragmatic Return to Effective Dental Infection Control through Triage and

Testing

PS Project Scientist, NIDCR, NIH

QA Quality Assurance
QC Quality Control
QoL Quality of Life

РΟ

SAE Serious Adverse Event/Serious Adverse Experience

SOP Standard Operating Procedure

UP Unanticipated Problem

US United States

WHO World Health Organization

Expiration Date:

PROTOCOL SUMMARY

Title: Pragmatic Return to Effective Dental Infection Control through Triage and

Testing

Précis: We will conduct a feasibility study to develop and test out procedures for

improved triage and COVID-19 testing of patients in dental practices to improve patient safety. This is one of several feasibility studies to be conducted in Rutgers dental clinics and in dental offices which participate in the National Dental Practice Based Research Network (PBRN). These studies will assess the feasibility of implementing COVID-related

procedures in the dental setting and may provide preliminary data to inform

a larger network-wide study grant application.

Objectives: Primary: The primary objective of this study is to determine patient

willingness to participate in a study and to test survey instruments and logistics developed for a NIH clinical study evaluating the impact of COVID-

19 testing and enhanced triage in dental offices.

Population: This study will take place at Rutgers University School of Dental Medicine.

Up to twenty (20) patients will be recruited in the Rutgers School of Dental Medicine's dental clinics. Only adults who are patients who are scheduled

for dental appointments will be recruited.

Number of Sites: One (1)

Description of Lab-processed saliva tests (Viral PCR SARS-CoV-2 tests) will be

administered to patients coming to the school for care. In addition, the use

of pulse oximeters will be added to the patient COVID-19 symptom triage

protocol.

Study Duration: Twelve (12) months

Subject Participation

Duration:

Intervention:

[figure not shown]
Two (2) weeks.

Estimated Time to Complete Enrollment:

Six (6) months

Expiration Date:

Schematic Study Design for Patient Subjects:

Expiration Date:

2 INTRODUCTION: BACKGROUND INFORMATION AND SCIENTIFIC RATIONALE

2.1 Background Information

Description of Problem:

The COVID-19 pandemic: COVID-19 has created serious concerns about the safety of patients and dental professionals as they return to a practice environment. The spread of this ubiquitous virus was first thought to be through droplets but soon it became clear that the virus could be spread by aerosols [5,6]. Many dental procedures require the mechanical preparation of hard and soft tissue using high speed handpieces which are water cooled and generate significant aerosolized sprays. The extent to which dentally-generated aerosols linger within operatories has not been clearly tested but it is certain that both dentists, dental assistants and hygienists will be exposed to significant aerosol sprays derived from patients' oral cavities [7]. As we learn more about COVID-19 and viral transmission we understand that infection and spread of the virus is due to the viral load (or dose) and the time of contact [8,9].

Uniqueness of Dental Practice: Unlike many procedures in medicine, dental/patient contact is eye to eye and the close proximity between patient and dental professionals is unavoidable [10]. Furthermore, a dental procedure can often take as long as 1 hour and prolonged close contact between dentist and patient is inevitable. Despite personal protective equipment (PPE) that includes N95 masks, face shields, gowns, and high-speed suction, viral spread from infected patients is unavoidable. This suggests that the only safe solution for maintaining the health and well-being of dental professionals in the time of COVID-19 is removing virus infected patients from their offices [11].

Waiting Rooms and Airflow: Obvious issues confronting dental practices have been discussed, however, waiting rooms with patients, bathrooms and passageways are all additional areas within offices that can be of concern. Further, the airflow in confined office spaces where patients can be waiting for 30 minutes or more can be hazardous if an asymptomatic but COVID-19 infected patient is in close proximity to a susceptible patient. Patients in a dental office can be at risk for infection that can have varied presentation and severity, and may be life threatening especially in patients with pre-existing conditions [21-23].

Solutions: One way of providing the security that dental offices are safe for both the dental professional and patient is by excluding anyone who harbors the COVID-19 virus. This of course would necessitate testing every patient at every visit or by establishing the fact that patients are safe if they have neutralizing antibody to the COVID-19 virus. These solutions, at this moment, appear to be impractical particularly if the virus affects a very small percentage of the population and testing is inaccurate. A solution to this problem is imperative both for the safety and security both the patient and dental professional. But what's to be done? How do we achieve our goal of providing a safe and secure environment that allows for routine dental care?

Several challenges exist to routine and comprehensive testing: the costs, turnaround time (maximum practical utility is perhaps derived from a simple, rapid, accurate, inexpensive point-of-care test that is not technically demanding, such a test has not yet been validated). This proposal compares the use of one such candidate POC test with the current screening gold-standard.

Conclusions: Every day that goes by, patients are not receiving dental services because of a COVID-19 transmission concern. Understanding risk associated with COVID-19 transmission in a dental practice and the effective use of testing and other practice modifications could dramatically reduce the risk, making both dental health care providers and patients comfortable with seeking/providing essential dental services. This proposal is designed to develop procedures that address this serious problem and test the feasibility of these procedures in a pragmatic manner to address this existing insurmountable problem that can affect the future of dental practice and the dental health we have come to expect.

2.2 Rationale

Typical dental protocols recommend twice yearly visits to dentists for prevention and maintenance of oral health [12,13]. Dental patients who may be asymptomatic for medical problems are seen routinely in dental offices and can be screened for the early phases of medical disease during routine dental visits. For example, blood pressure monitoring and simple blood test for glycosylated hemoglobin (HbA1c) levels can be performed in dental offices for referral to physicians for further assessment [18,19]. This ready access to vulnerable patients can be considered as value-added should dental health professionals provide augmented diagnostic benefit to patients who are unaware of their need for medical intervention. However, in this time of uncertainty dentistry has been impacted by fear and poorly defined strategies to mitigate COVID-19, that can compromise the willingness of dental professionals to open their dental practices [20].

Little is Known Regarding the Effectiveness COVID-19 Triage in Dental Practice: Little is known about the effectiveness of triage protocols which have been recommended by the CDC. For example, most offices are using temporal thermometers yet many are uncalibrated. In addition, screening questions continue to evolve and the veracity of patient responses remains unverified

Little is Known Regarding the Impact of COVID-19 Testing in Dental Practice: Little is known about the value of testing and about the willingness of DHCW to implement COVID-19 testing in a dental office or the most effective use of such testing.

Ultimately, we will perform three feasibility studies (Two patient and one DHCW study) which examine the following questions:

- Perception of safety and comfort: Will patients and DHCW in an office with either LAB or POC testing feel safer and be more comfortable delivering care during a COVID-19 or other infectious disease pandemic?
- Testing preference: Do DHCW and patients prefer POC testing rather than testing that requires laboratory processing?
- Effectiveness of triage: Is the triage protocol being followed today effective or do patients and DHCW respond negatively to COVID-19 symptoms because of the fear of not being seen or being turned away from work?
- Effectiveness of triage methods: Are objective measures such as temperature and pulse oximeter readings effective in identifying "asymptomatic" cases?

2.3 Rationale

2.3.1 Potential Risks

This research involves testing procedures with varying degrees of risk to the study participants.

• Saliva Test- minimal risk. The saliva test is non-invasive, requires spitting into a tube, and is completed independently, without interaction with a member of the healthcare team.

In addition, different COVID-19 test types have varying degrees of sensitivity and specificity, which may result in false negative and false positive test results. While a false negative result may give a participant a false sense of security, this would not pose additional risks to patients or the DHCWs in the dental practice, as the patient would have been treated according to the office's infection control protocol regardless of participation in the study. On the other hand, a false positive result will prompt the patient to undergo additional testing by their primary health care provider. Should they test positive again, they would need to follow their local health department recommendations which may require quarantine.

There is a risk of loss of confidentiality for all study participants. Precautions will be in place to minimize this risk, such as collecting only minimal identifying information, using unique study codes for participants,

collecting data using encrypted computers, and maintaining electronic data files on a password-protected computer drive, and storing data on encrypted computers or in locked cabinets (located in locked offices). Individual identifier numbers that are linked to participant contact information will be stored separately from the data. Compliance with all IRB regulations concerning data collection, data analysis, data storage, and data destruction will be strictly observed.

2.3.2 Potential Benefits

There is no benefit to patients participating in this study beyond the fact that patients would receive the results of the free COVID-19 tests they undergo.

Expiration Date:

3 OBJECTIVES AND OUTCOME MEASURES

3.0 Rutgers Feasibility Study Outcomes

PILOT Objectives	Brief Description/Justification of Outcome Measure	Outcome Measured By	Time Frame
To Determine Patient Willingness to Participate	Willingness to participate is important in determining whether patients would be willing to participate in a large-scale study	Ratio of patients agreeing to participate as compared to all patients asked to participate Thoroughness of consent process and ability to ask questions	Willingness to Participate: Patients – at time of consent by patients Patients – at End-of-Study
To Determine Patient Willingness/Ability to Follow Thru with Triage, Testing and Survey Administration Procedures	Determining willingness and ability to follow thru with triage, testing and survey administration procedures is important for refining the survey procedures	% who complete the study % who complete surveys o Pre-Visit Patient Survey o End-of-Visit Patient Survey % who feel testing (Saliva procedure was easy to comply with o Specimen collection o Specimen preparation for shipping o Specimen storage o Timeliness of results o Reporting of results	% Complete Study: Patients – End-Of-Visit (Day 1) % All Surveys Completed: Patients – End-Of-Visit (Day 1) % Feel Testing Protocol was Easy to Comply With: Patients – End-Of-Visit (Day 1)
To Determine Ease of Use with REDCap Survey Instruments Patient Subject Start-of-Visit Survey End-of-Visit Survey Triage Survey	Determining the ease of use and completeness of the REDCap instruments enables refinement of the system	% who feel surveys are easy to complete due to administration method:	% indicating surveys were easy to complete due to administration method: • Patients – at end of patient visit % indicating survey questions were easy to understand: • Patients – End-Of-Visit (Day 1) % Surveys Completed: • Patients – End-Of-Visit (Day 1)

3.1 Primary Outcomes for Full Study (Data Collection is Being Performed to Determine Instrument Feasibility)

Full Study Objective	Brief Description/Justification of Outcome Measure	Outcome Measured By	Time Frame
Objective 1 – Dental health care personnel and patients feel safe in the dental office	Patient Safety and Comfort Survey asks patients their concerns about seeing their dentist and their perceptions about the value of different safety precautions. Willingness to Return for another Visit reflects a patient's comfort with safety practices employed by their dentist. Willingness to Refer Other Patients reflects a patient's or DHCW's safety of the dental practice.	Patients: Patient Safety and Comfort Survey 4 Items asking about concern on a 4 point Likert Scale – 1=not concerned at all, 2= mild concern 3=moderate concern, 4= severe concern 6 Items asking about safety on a 3 point scale – Not at All, Not Sure, yes 5 Items asking about Importance of safety practices on a 5 point Likert Scale – 1=extremely important, 2=important, 3 = Not important or unimportant, 4 = unimportant, 5 = very unimportant How safe to do feel coming to work? 5 Point Likert scale Patients – Willingness to Return for another Visit: How likely are you to return for another visit within the next 12 months? 5 Point Likert Scale Willingness to Refer Other Patients: How likely would you refer a family or friend to this dental office? 5 Point Likert Scale	Sense of Safety for Patients: Day prior to visit At end of visit Willingness to Refer Other Patients: LAB Patients - Day prior to visit All Patients - end of visit

3.2 Secondary Outcomes for Full Study (Data Collection is Being Performed to Determine Instrument Feasibility)

Objective	Brief Description/ Justification of Outcome Measure	Outcome Measured By	Time Frame
Objective 2: Determine the Efficiency and Effectiveness of: • Efficiency of Patient Triage Protocols • Effectiveness of LAB	Efficiency of Triage Protocols:	Efficiency of Triage Protocols: Time needed to complete triage survey Effectiveness of Triage Protocols Comparison of number of patients not able to have visit completed Comparison of Triage Survey to Medical History consistent with COVID-19 symptoms for DHCW Efficiency of Testing Protocols: Time and supplies needed to conduct LAB Effectiveness of Testing Protocols Number of patients not able to report for their patient visits LAB offices	Efficiency of Triage Protocols: LAB Patients: Start of visit Effectiveness of Triage Protocols Patients: End of visit Efficiency of Testing Protocols: Patients: End-of-Visit

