4 STUDY DESIGN

Description: This study will assess the feasibility of implementing one COVID-related testing procedure in the dental setting. Results from this study may provide preliminary data to inform a larger network-wide study grant application.

Study Population: The study population for this study will be patients seen at the Rutgers School of Dental Medicine.

Important Outcomes: For this study, important outcomes include percent of patients willing to participate and percent completing the protocol.

Single or Multicenter: Single- this study will utilize the Rutgers School of Dental Medicine's Newark facility.

Number of Study Groups/Arms: One (1)

Expected Duration of Subject Participation: Subjects will be actively participating in the study for 2 weeks.

Sequence of Procedures and Duration of Study Period: Consent Process

About two weeks prior to their scheduled dental visit, patients will be contacted by the dental office to determine their willingness to participate in the study. Patients who indicate interest will be sent an email link, which opens the consent. The consent will clearly outline participant expectations and offer the opportunity for potential participants to contact the office for more information as needed. Participants who fully understand the study and elect to participate will affirm their willingness to participate by clicking the "I agree to take part in this study" button at the end of the consent form. Once in the office to provide their saliva sample, patients will also be asked to provide signed informed consent.

Study Procedures

Study participants will be asked to do the following:

- Two weeks before the dental visit
 - o Complete an electronic survey: Patient Pre-Visit Survey
 - Questions explore perceptions of safety and comfort, reasons for delaying dental care, concerns about returning to dental care, safety precautions valued, importance of triage and testing, and demographics
 - Launched automatically after the completed consent
 - Receive a saliva collection kit by mail
- One week before the dental visit
 - o Complete a COVID-19 saliva test
 - Spit into a tube
 - Package as directed
 - Drop off the completed test kit at the dentist's office
- Day prior to the dental visit
 - Undergo a COVID-19 triage screening over the phone*
 - Screening includes symptom questions (presence or absence of):
 - fever or chills
 - cough
 - shortness of breath or difficulty breathing
 - fatigue
 - muscle and body aches

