 - headache
 - loss of taste

[figure not shown]
- loss of smell
- sore throat
- congestion or runny nose
- nausea or vomiting
- diarrhea
- At the start of the Dental Visit
 - Undergo a COVID-19 triage screening in the office*
 - Screening includes symptom questions, temperature check, and pulse oximeter reading
- At the End of the Dental Visit
 - Complete two electronic surveys
 - Patient End-of-Visit Survey
 - Questions explore perceptions with testing preferences, PPE observed, environmental controls observed, concerns about returning to dental care, safety precautions valued, importance of triage and testing, likelihood of reporting symptoms, dentists role in COVID-19 testing and vaccinations
 - Patient Participation Survey
 - Questions explore perceptions related to study participation including survey and testing logistics

If any aspect of the COVID-19 triage screening is positive, appointment will be postponed and the participant will be referred to their primary care physician for further testing.

- A Positive screening by reporting one or more symptoms
- A positive temperature is considered greater than 100.4 degrees F
- A positive pulse oximeter is considered when the blood oxygen saturation level is below 95%

The results of the lab processed COVID-19 test will be reported to the Clinic Director or one of the coinvestigators by the lab prior to the scheduled dental visit. Results will be recorded in the *Testing Case Report* form in REDCap.

- If **POSITVE**: The Clinic Director or one of the co-investigators will communicate positive results to the participant upon receipt. Positive participants will be instructed to consult with their primary care provider for further testing.
- If NEGATIVE: The Clinic Director or one of the co-investigators will communicate negative results to
 the participant by phone on the day prior to the dental visit after the COVID-19 triage screening is
 performed.

Methods for Data Collection

REDCap will be used to collect and maintain all study data. For all surveys and case reports, the Research Clinical Director or co-investigator will enter data directly into REDCap. Surveys will be entered by the patient with the Clinical Director or co-investigator's assistance.

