11.3 Final Analysis Plan

Data to be collected includes:

Item	Type of Variable
Willingness to Participate	 Willingness to participate (Binary – Yes/No)
Patient willingness to participate	
Triage Survey	Ease of Administration (3 point Likert Scale) Very easy to complete survey due to administration method Easy to administer complete survey due to administration method Not easy to complete survey due to survey administration method Completeness (Binary – Yes/No) Question understandability (3 point Likert Scale) Very clear to understand Understandable with some clarification provided by the administrator Not clear to understand
Safety Perception Survey	
Start-of-Visit Patient Survey End-of-Visit Patient Survey	Administration method (3 point Likert Scale) Very easy to complete survey due to administration method Easy to complete survey due to administration method Not easy to complete survey due to administration method
	 Completeness (Binary – Yes/No)
	 Question understandability (3 point Likert Scale) Very clear to understand Understandable with some clarification provided by the administrator Not clear to understand
Testing Logistics	Specimen Collection (3 point Likert Scale)
LAB – saliva SARS-CoV-2 viral test	 Very easy to collect Easy to collect Not easy to collect Specimen preparation for shipping (3 point Likert Scale) Very easy to prepare Easy to prepare Not easy to prepare Specimen storage (Binary – Easy/Not Easy) Easy to Store Not easy to store

	Timeliness of results (3 point Likert Scale) Very timeless access to results Timely access to results Access to results not timely Reporting of results (3 point Likert Scale) Very easy to access results Easy to access results Not easy to access results	
Testing Case Report	 Completeness (Binary – Yes/No) 	

Descriptive statistics (frequencies) for all variables will be analyzed.

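### The Day -14 survey and, it appears, the consent process are rated only at or after the dental visit, so the ratings come late and mainly from patients who reach it

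*Combined protocol and SAP*

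**What the plan says.** **When the steps happen.** Section 6.1 puts electronic consent and the Pre-Visit Patient Survey at Day -14 (+/- 7). In Section 4 the consent opens from an emailed link and the survey is "Launched automatically after the completed consent". The consent signature is taken later, in the office, at Day -7 (+/- 5).

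**When they are rated.** Section 3.0 takes the ease-of-completion rating "Patients – at end of patient visit". The percentage "indicating survey questions were easy to understand" is also an end-of-visit, Day 1 measure. For the willingness objective, which includes "Thoroughness of consent process and ability to ask questions", the time-frame cell reads "Patients – at time of consent by patients Patients – at End-of-Study".

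**Which instrument collects the opinions.** Section 4 describes one instrument covering views on taking part, the Patient Participation Survey: "Questions explore perceptions related to study participation including survey and testing logistics". Sections 4 and 6.1 and Appendix A place it at the dental visit. Section 7.1 places it at end of study, Day 28.

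**How they are analysed.** Section 11.3 lists three-point scales for ease and clarity and plans frequencies, without naming denominators. The middle clarity option is "Understandable with some clarification provided by the administrator". No variable is listed for the consent process.

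**The concern.** The Protocol Summary gives testing the survey instruments and logistics as part of the primary objective, so ease and clarity ratings are part of what this pilot is meant to produce. Two things weaken them for the early steps.

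First, patients rate from memory, after a dental visit and two further surveys or triage contacts have intervened. Second, only patients who get as far as the visit are asked on schedule. If those who found the early survey difficult are more likely to leave, the ratings will look better than the experience was, and the larger study will inherit problems that nobody reported.

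The response scale adds a smaller problem. For a survey opened from an email link, a middle option that presumes help from an administrator may not describe what happened to a patient who worked alone.

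**Working it through.** The plan gives no figure to reproduce on this point: no sample size calculation, no attrition rate and no target for the ratings. The checks are day counts and a comparison of sections.

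**1. Delay between step and rating.** Lag = rating day minus step day.

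| Step (window) | Rated Day 1 | Rated Day 28 |
|---|---|---|
| E-consent and Day -14 survey (Day -21 to Day -7) | 1 - (-21) = 22; 1 - (-14) = 15; 1 - (-7) = 8 | 28 + 21 = 49; 28 + 14 = 42; 28 + 7 = 35 |
| Signed consent (Day -12 to Day -2) | 1 + 12 = 13; 1 + 7 = 8; 1 + 2 = 3 | 28 + 12 = 40; 28 + 7 = 35; 28 + 2 = 30 |

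If the calendar has no Day 0, each lag is one day shorter. The Day 28 column applies only if the single Section 7.1 entry governs.

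**2. Is anything asked earlier?** The schedules in Sections 6.1 and 7.1 and Appendix A show no rating item at Day -14 or Day -7.

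**3. Who is missed.**
- Withdrawers: Section 6.2 has no withdrawal visit. Section 5.4.2 stops procedures, records the date and reason, and does not replace the patient.
- Silent drop-outs: no route for an opinion is described.
- Patients with a positive test or triage result: under Section 7 they are not seen at the scheduled visit, which is rebooked after recovery, so their ratings are delayed or lost.

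**4. What a lost rating is worth.** With the Section 5.3 target of 20, one rating is 1/20 = 5 points. Suppose all 20 finish the Day -14 survey, k of them are never rated, and every rated patient is favourable. The reported figure is then 100%, while the figure for all 20 lies between (20 - k)/20 and 100%:
- k = 0: no gap
- k = 1: 95% to 100%
- k = 2: 90% to 100%
- k = 4: 80% to 100%

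These values of k are assumed; they give bounds, not estimates. For scale, an observed 18/20 has an exact 95% interval of 68.3% to 98.8%, so one or two lost ratings matter less than sampling error.

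**5. Which survey is rated?**
- Section 3.0, completion objective: Pre-Visit and End-of-Visit.
- Section 3.0, ease-of-use objective, and Section 11.3: Start-of-Visit, End-of-Visit and Triage.
- Section 6.1: Pre-Visit at Day -14, Start-of-Visit at Day 1.
- Section 7.1: Start-of-Visit at Day 1.
- Section 12: Pre-Visit, with no Start-of-Visit form.
- Appendix A: Start-of-Visit at Day -14.

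If the two names mean one survey, it is rated 8 to 22 days late. If they are two surveys, the Day -14 survey has no ease or clarity rating at all.

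**The case against.** **Much of the information on leavers is captured elsewhere.** This stands. Refusals enter the participation ratio, leavers lower the completion percentages, Section 5.4.2 records withdrawers' reasons by interview, and Section 13 makes incomplete surveys an outcome. What is missing is the ease, clarity and consent ratings themselves, and any reason from silent drop-outs.

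**A later rating covers the whole consent process.** This also stands. Section 14.3 treats consent as continuing and has staff explain the study and answer questions, and the signature comes after the e-consent. Simply moving the consent item to Day -14 would miss the in-office stage. A later consent item should be kept.

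**The consent timing is uncertain.** Pairing the consent opinion with end of study is inferred from a table flattened in text extraction, and Section 3.0 does not say outright that it is a patient rating. The survey ratings do not depend on this inference.

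**A reader might infer that nobody is available to help when the Day -14 survey is opened.** The documents do not support that. Section 4 says patients enter surveys with staff assistance and lets them contact the office about the consent. Section 7.1, however, calls the Start-of-Visit Survey self-administered. The text is in tension, and the middle clarity option fails only for patients who complete the survey alone.

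**A reader might also infer that earlier rating would capture those who left because consent or the survey was poor.** It would not. The survey opens only after e-consent is completed, and a last-page item is seen only by those who get there. The gain is limited to patients who finish a step and are lost afterwards.

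**Conclusion.** The point holds as a modest, inexpensive improvement. On the reading that the Pre-Visit and Start-of-Visit names refer to one survey, the Day -14 survey is rated 8 to 22 days after completion (15 nominal), and mainly by patients who reach the visit. On the other reading it is not rated for ease or clarity at all. The consent opinion appears to share the delay, subject to the table inference above.

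The size and direction of any bias cannot be established. Each lost rating is worth about 5 points at 20 patients. The ratings would be too favourable only if those lost were less satisfied than those kept; losses through a positive test or triage result may be unrelated to satisfaction and would then cost mainly numbers. A reader might infer a specific overstatement of ease or clarity, but without an attrition figure the documents support none.

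Nothing here invalidates a descriptive feasibility study. It does mean that feedback the study was set up to gather would be recalled late and, for some patients, lost.

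**What to change.** 1. Put the ease and clarity items for the Day -14 survey on its last page.
2. Ask a short item about the e-consent on that survey's first page, and keep a later consent item after the in-office signature, so that both stages are covered.
3. For this survey, replace the middle clarity option with one that needs no administrator, such as *some questions were unclear*, and state whether staff assist with it.
4. Report each rating with the number who completed that step as the denominator, and show how many gave no rating.
5. List the consent items, with their scales, in Section 11.3.
6. Reconcile the Pre-Visit and Start-of-Visit names and timing across Sections 3.0, 6.1, 7.1, 11.3 and 12 and Appendix A, and the Day 1 versus Day 28 timing of the Participation Questionnaire.

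The end-of-visit questionnaire stays for the later steps. The cost is about one extra minute for the patient, a few more REDCap items, and text edits. People who decline or abandon the consent, or who stop partway through the survey and never reach its rating items, will still not give those ratings; the report should say so.
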